### **Pregnancy and Comorbid Conditions**

The number and percentages of patients with positive results will be reported for the following tests, if performed at baseline: pregnancy, HIV, hepatitis B, hepatitis C, tuberculosis, and **CCI** tests.

### **12 Previous **CCI** Medications**

This section describes how previous medications **CCI** will be summarized. Medications started prior to the start of the study dose are referred to as previous medications. Medications that were started prior to the study dose **CCI** are referred to as concomitant medications.

**CCI**

CCI

## 13

## Study Dose Compliance and Exposure

All dosing calculations and summaries will be based on the “Exposure” eCRFs pages.

The FAS (i.e., Safety) population will be used for the related summaries.

The number of planned 10-mg tablets will be determined as follows (where weight is in kg and refers to the baseline weight).

For patients in the initial treatment course in Year 1, for each treatment week:

1. *If weight < 110, then ‘Number of planned tablets’ = nearest integer to (weight – 5)/10*
2. *If weight ≥ 110, then ‘Number of planned tablets’ = 10*

---

For patients in the second treatment course in Year 2, for each treatment week:

1. If weight < 80, then 'Number of planned tablets' = nearest integer to  $(\text{weight} - 5)/10$
2. If weight  $\geq 80$  and weight < 110, then 'Number of planned tablets' = nearest integer to  $(\text{weight} - 15)/10$
3. If weight  $\geq 110$  then 'Number of planned tablets' = 10

The planned dose (mg) is given by 'Number of planned tablets' \* 10.

The planned dose (mg/kg) is given by 'planned dose (mg)' / weight.

For each treatment week, the actual number of tablets received is given by the 'Number of tablets' as recorded through the eCRF forms.

The actual dose (mg) is given by 'actual number of tablets' \* 10.

The actual dose (mg/kg) is given by 'actual dose (mg)' / weight.

Treatment adherence is one of the secondary endpoints and will be assessed through a questionnaire. It is described in Section 16.4.

Data on cladribine tablet treatment during the study period will be collected, including medication start dates, medication stop dates, medication dose (mg), number of doses, and reasons for discontinuation, if applicable. A listing with at least the following characteristics will be presented:

- Patient ID
- Cladribine tablets start date
- Cladribine tablets stop date
- Visit
- Planned number of tablets
- Actual number of tablets
- Planned dose (mg/kg)
- Actual dose (mg/kg)
- Treatment compliance (%)
- Reason for dose adjustment
- Reason for no dose

The number of planned tablets, the planned dose (mg/kg), and the actual dose (mg/kg) will be provided. Treatment compliance (%) is defined as the total actual number of cladribine tablets / total planned number of cladribine tablets.

---

The number and percentage of patients who discontinue cladribine tablets will be reported.

The number and percentage of patients who started other MS treatments after discontinuation of cladribine tablets will be reported (using the number of patients who discontinue cladribine tablets as the denominator).

Reasons for discontinuation of cladribine tablets will be collected, and, for each reason, the corresponding number and percentage of patients will be reported (using the number of patients who discontinue cladribine tablets as the denominator).

A listing of concomitant MS medications started after discontinuation of cladribine tablets will be provided. The following variables will be reported:

- Patient ID
- Medication name
- Visit
- Dose
- Unit
- Frequency
- Route of administration
- Start date / ongoing (Yes/No) / stop date
- Last study treatment administration date

The elapsed time to discontinuation of cladribine tablets will be calculated as follows:

*Elapsed time to discontinuation of cladribine tablets = Date of discontinuation of cladribine tablets – Date of first study dose*

It will be summarized as a continuous variable and also reported through KM analysis. The ‘Last study treatment administration date’ according to the treatment termination form will be used as the date of discontinuation of cladribine tablets both for patients discontinuing the treatment early and for patients who complete treatment (for patients completing treatment, this will be a censoring date).

The number of doses and % of planned doses (as per USPI) received will be summarized descriptively.

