9.2.2 Definition of Study Cohorts and Description of Treatments

The study will have a single primary cohort that consists of all patients enrolled in the study who received at least 1 dose of cladribine tablets. Additionally, a sub-cohort of approximately 100 patients that directly switched from ocrelizumab to cladribine tablets will be prospectively enrolled. All treatment and other medical decisions will be made by the investigator, with no directives mandated by this study protocol.

All study patients are anticipated to receive marketed cladribine tablets as per investigator discretion and as per US approved label: 3.5 mg/kg body weight over 2 years, administered as 1 treatment course of 1.75 mg/kg per year. Each treatment course consists of 2 treatment weeks, 1 at the beginning of the first month and 1 at the beginning of the second month of the respective year. Each treatment week consists of 4 or 5 days on which a patient receives 10 mg or 20 mg (1 or 2 tablets) as a single daily dose, depending on body weight. Since prescribing is determined by the investigator as per standard of care and according to the USPI, the benefits and risks to patients in being in the study are not different than the benefits and risks to patients taking cladribine tablets as per standard of care and according to the USPI in the general population.

Following completion of the 2 treatment courses, do not administer additional cladribine tablet treatment during the next 2 years, as stated in the USPI.

As per USPI, ALC values need to be normal at the initiation of cladribine tablets in Year 1, and ALC results need to indicate ≥ 800 cells per microliter at the start of the Year 2 treatment course. If necessary, the Year 2 treatment course should be delayed for up to 6 months to allow for recovery of lymphocytes to ≥ 800 cells per microliter. If this recovery takes more than 6 months, the patient should not receive further treatment with cladribine tablets.

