### **6.4                    Third Interim Analysis**

The third interim analysis will be performed on the 12-month data for all patients.

This analysis will include all the endpoint analyses related to the objectives of the study. For the PROs, the actual value at each visit and the change in scores from Baseline to Months 6 and 12 will be considered. This analysis will allow interim assessment of all relevant aspects of the study.

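### For baseline weight 80 to <110 kg, the SAP plans two more tablets in the Year 1 course than in the Year 2 course, although the protocol sets equal yearly courses

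*SAP*

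**What the plan says.** Protocol 9.2.2 describes the labelled regimen as "3.5 mg/kg body weight over 2 years, administered as 1 treatment course of 1.75 mg/kg per year", and adds: "Each treatment course consists of 2 treatment weeks".

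SAP Section 13 turns this into tablets: "The number of planned 10-mg tablets will be determined as follows", with the qualification "where weight is in kg and refers to the baseline weight". There are two rules, both per treatment week:

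- The Year 1 rule is introduced by "For patients in the initial treatment course in Year 1, for each treatment week". Below 110 kg it is the nearest integer to (weight − 5)/10. From 110 kg it is 10.
- The Year 2 rule is introduced by "For patients in the second treatment course in Year 2, for each treatment week". Below 80 kg it is the nearest integer to (weight − 5)/10. From 80 to <110 kg it is the nearest integer to (weight − 15)/10. From 110 kg it is 10.

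Planned mg and mg/kg are derived from these counts. The Section 13 listing has columns for visit, planned and actual tablets, planned and actual mg/kg, and compliance. On compliance the text says: "Treatment compliance (%) is defined as the total actual number of cladribine tablets / total planned number of cladribine tablets".

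**The concern.** Both rules take the same input, baseline weight, and the protocol dose is the same each year, so the two planned courses should match. They match everywhere except from 80 to <110 kg, where Year 2 loses one tablet in each of its two weeks. The one-tablet step is attached to the year rather than to a week within the course.

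Planned tablets and planned mg/kg by week and by year feed directly into outputs that Section 13 says will be provided. If compliance is also shown by visit or course, patients in this band who followed the label would appear under-dosed in Year 1 and over-dosed in Year 2. The same distortion enters any compliance figure whose denominator holds Year 1 only. One example is the interim described in SAP 6.4 ("The third interim analysis will be performed on the 12-month data for all patients"). Another is a patient who stops after Year 1, if an unstarted Year 2 course is not counted as planned.

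**Working it through.** **Inputs.** Dose 1.75 mg/kg per yearly course, 3.5 mg/kg in total, and 2 weeks per course (protocol 9.2.2). Tablet strength 10 mg, baseline weight in both years, and the two formulas (SAP 13). Halves are rounded up.

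**Formulas.** Tablets per course = 2 × tablets per week. Dose in mg/kg = tablets × 10 / weight.

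**The SAP's planned doses.**

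| Weight (kg) | Per week, Y1 / Y2 | Per course, Y1 / Y2 | mg/kg, Y1 / Y2 | Two-year mg/kg |
|---|---|---|---|---|
| 75 | 7 / 7 | 14 / 14 | 1.87 / 1.87 | 3.73 |
| 85 | 8 / 7 | 16 / 14 | 160/85 = 1.88 / 140/85 = 1.65 | 300/85 = 3.53 |
| 95 | 9 / 8 | 18 / 16 | 180/95 = 1.89 / 160/95 = 1.68 | 340/95 = 3.58 |
| 105 | 10 / 9 | 20 / 18 | 200/105 = 1.90 / 180/105 = 1.71 | 380/105 = 3.62 |
| 110 | 10 / 10 | 20 / 20 | 1.82 / 1.82 | 3.64 |

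On a 0.1 kg grid from 80 to <110 kg, the gap is 2 tablets at every weight. Year 1 averages 1.90 mg/kg (range 1.78–2.00) and Year 2 averages 1.68 (range 1.56–1.80). Below 80 kg and from 110 kg the gap is zero.

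**Can rounding explain it?** No. Halving the SAP's own two-year totals gives whole-tablet equal courses in every band: 30/2 = 15, 34/2 = 17, 38/2 = 19. These average 1.79 mg/kg over the band.

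**Where the error probably lies.** The totals of 15, 17 and 19 are odd, so the two weeks of a course must differ by one tablet: 8+7, 9+8, 10+9. Those pairs are exactly what (weight − 5)/10 and (weight − 15)/10 produce. The SAP's Year 2 plan is also the same 14 tablets at 75 kg and at 85 kg, while Year 1 rises from 14 to 16. Both features suggest that a rule for one week of each course was assigned to Year 2.

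**Apparent compliance of a fully adherent patient, if the true courses are 15, 17 and 19 tablets.**

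- Year 1 course: 15/16 = 93.8%, 17/18 = 94.4%, 19/20 = 95.0%.
- Year 2 course: 15/14 = 107.1%, 17/16 = 106.25%, 19/18 = 105.6%.
- Lower-dose week of Year 1: 7/8 = 87.5%, 8/9 = 88.9%, 9/10 = 90.0%.
- Higher-dose week of Year 2: 8/7 = 114.3%, 9/8 = 112.5%, 10/9 = 111.1%.
- Both courses: 30/30, 34/34, 38/38 = 100%.
- Stopped after a full Year 1 course: 93.8–95.0% if only Year 1 counts as planned. If both courses count, 15/30 = 50%, which the error does not change.

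**The case against.** The arithmetic is not in dispute; the case on the other side is about certainty and reach.

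- **The label table is not in the documents.** The true weekly counts, and so every compliance percentage above, rest on the assumed 15/17/19-tablet courses. This stands for the percentages and the week order. It does not touch the mismatch between years, which follows from the protocol and SAP alone.
- **1.75 mg/kg is nominal.** Bands not in question also depart from it: the formula gives 2.00 mg/kg at 40, 50, 60 or 70 kg and 1.60 just under 50 kg. This stands too. A deviation from 1.75 proves nothing by itself; the evidence is that the same patient at the same recorded weight gets two different planned courses.
- **Compliance is defined on totals.** Over two planned courses the error cancels. The SAP does not explicitly define compliance by week or course, and the compliance column in the listing may hold a patient total. The compliance consequences are therefore conditional. The planned-tablet and planned mg/kg errors are not.
- **The 12-month interim is probably past.** The last patient consented on 28 November 2022, and this SAP version is dated 23 January 2025. That limits the practical effect on that interim but does not correct the final planned-dose outputs.

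One point extends the reach. Compliance is a variable in the multiple-imputation model of SAP 14.1.4. If its denominator is Year 1 only, values for affected patients would be shifted by about 5 to 6 percentage points.

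**Conclusion.** The point holds and should be corrected. For baseline weight 80 to <110 kg, SAP 13 plans two tablets more in Year 1 than in Year 2, contrary to the equal yearly courses in protocol 9.2.2. Planned tablets and planned mg/kg by week and year are wrong for this band. Course or week compliance, where shown, is wrong with them, as is compliance on a Year 1-only denominator.

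Total compliance over both planned courses, actual tablets, actual mg/kg, the per-protocol set and the primary ARR estimate are not affected. Confidence is high for the asymmetry. The diagnosis of a misassigned week rule is an inference from the SAP's own totals, to be confirmed against the USPI. The documents do not give the share of patients in the band, so the effect on summary tables cannot be sized.

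**What to change.** In SAP 13, key the planned-tablet formula to treatment week within course and use it identically in both years. For 80 to <110 kg, plan one week at the nearest integer to (weight − 5)/10 and the other at the nearest integer to (weight − 15)/10, giving 15, 17 or 19 tablets per course. Confirm the counts and the week order against the USPI dosing table before finalising. Leave the rules below 80 kg and from 110 kg unchanged.

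State whether the total planned tablets include a Year 2 course that was never started, and apply the same definition to the compliance variable in the imputation model.

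The cost is a few lines of SAP text and code, plus a rerun of the planned-dose and compliance tables and listing. No new data are needed.

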In accordance with the USPI, it is anticipated that patients may not receive their second course of cladribine tablets precisely 12 months after the initiation of cladribine tablets owing to ALC levels <800 cells per microliter or other potential clinical factors. In the event that the second course of cladribine tablets is delayed beyond Month 13, the PRO only collection scheduled for Month 13 should be adjusted to occur during the start of the second course of cladribine tablets. The timing of Visit 4 (Month 14) and the subsequent visits may need to be adjusted based upon the actual start date of the second course of cladribine tablets, which will be recorded by the investigator.

Table 1. Schedule of Assessments

Assessments	Data collection time points (as expected based on routine clinical practice)									
	Pre-baseline Screening Visit	Baseline Visit ^a	PRO Only ^b	Visit #1	Visit #2	Visit #3	PRO Only ^b	Visit #4	Visit #5	Visit #6
(Days -60 to 0)	Month 0	Month 1	Month 2	Month 6	Month 12	Month 13	Month 14	Month 18	Month 24 ^j	
Informed consent	X									
Medical history, previous relapses, previous DMD treatment		X								
Inclusion / exclusion criteria	X									
Demographic data	X									
Pregnancy test, HIV, hepatitis B and hepatitis C and tuberculosis status		X				X				
Cladribine tablets ^c		X		X		X		X		
Other MS DMD during study period, if applicable				X		X		X		X
Neurological examination as per standard of care		X			X	X			X	X
Physical examination as per standard of care		X								
Relapse count (prospective) ^d						X				X
MRI documentation ^e		X			X	X			X	X
Hematology assessment (ALC, CBC, lymphocyte subsets, immunoglobulins) ^f		X		X	X	X		X	X	X
Patient-reported outcomes										
Treatment adherence ^g		X ^h	X	X			X	X		
TSQM		X ^h			X	X				X
SF-36		X ^h			X	X				X

Company substance code: 700568
Protocol number: MS700568_0079

^a Duration between end of previous treatment and start of cladribine tablets is at the discretion of the investigator.

^b At the PRO only time point, patients fill out the PROs at their home; patients do not come to the clinic for filling out PROs at these time points.

^c Cladribine tablets are expected to be taken according to the USPI. If cladribine tablets are discontinued, reasons for discontinuation and follow-up MS treatment will be collected.

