9.3 Variables

The following variables will be collected:

Screening and/or Baseline Visit

- Patient demographics, including: age, sex, weight, self-reported race/ethnicity
- Date of diagnosis of MS, date of first symptoms of MS
- DMD treatments received prior to study enrollment, since MS diagnosis (including medication doses and routes of administration, start dates, stop dates, and reasons for discontinuation)
- Relapse of MS in the 2 years prior to the study period or since MS diagnosis, if diagnosis <24 months (including dates of onset and resolution of relapse)
- Most recent MRI results prior to starting cladribine tablets (baseline MRI), which is expected to have been taken within the prior 90 days
[REDACTED]
[REDACTED]
[REDACTED]
- Results of MRI in the 2 years prior to study enrollment or since MS diagnosis, if diagnosis <24 months
[REDACTED]
[REDACTED]
- Results of neurological examination as per standard of care (e.g., Kurtzke Functional System Scores (FSS), ambulation up to 500 meters and Expanded Disability Status Score [EDSS])
- Results of physical examination as per standard of care
- Hematology assessment (white blood cell count, hemoglobin, hematocrit, platelet count, ALC). If the investigator assesses
[REDACTED] or immunoglobulin levels, these data should be recorded as well
- Pregnancy, human immunodeficiency virus (HIV), hepatitis B, hepatitis C and tuberculosis test results
- ePRO assessments (treatment adherence questions based on modified versions of the MS-TAQ, TSQM, SF-36, MFIS-5, BDI-FS, WPAI-MS, PDDS)
- Comorbid conditions
- List of all MS symptomatic specific medications taken in the 2 years prior to study enrollment (or since MS diagnosis, if diagnosis <24 months), including medication start and stop dates and reasons for discontinuation

Follow-Up Visits

The anticipated timing of assessments is presented in Table 1: Schedule of Assessments.

- Medication log of cladribine tablets treatment during the study period, including medication start dates, medication stop dates, medication dose (mg), number of dose and reasons for discontinuation
- Medication log containing other MS DMD treatments (if applicable) during the study period, including medication doses and routes of administration, start dates, stop dates and reasons for discontinuation

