## Overview of Planned Analyses

There will be a baseline analysis, 3 interim analyses, and a final analysis. Baseline and interim analyses are descriptive and for monitoring purposes. Multiplicity corrections will not be considered. Statistical analyses will be performed using the Electronic Case Report Form (eCRF) data gained until the cutoff dates described in the following subsections.

If the start of cladribine Year 2 treatment needs to be delayed (e.g., to allow for lymphocyte recovery to at least 800 cells/mL), all Year 2 visits and procedures will be moved out accordingly (at most 6 months). If recovery to 800 cells/mL is not complete after the 6-month delay, Year 2 treatment should not be initiated; the patient will nonetheless be followed up until the end of the observation period.

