### Subgroups:

The following subgroups will be defined:

- Patients completing the 24-month study
- Patients not completing the 24-month study (i.e., lost to follow-up, withdrawing consent, protocol deviations)
- Patients not completing the treatment (i.e., completing Year 1 treatment but not Year 2 treatment, or not completing both courses of treatment each year)
- Type of MS at screening: RRMS, aSPMS, PPMS, CIS
- Patients diagnosed with MS <24 months before transitioning to cladribine tablets
- Centers
  - Pooling of centers: Because of the high number of participating centers and the anticipated small number of patients in each center, data will be pooled across centers,

and the factor centers will not be considered in statistical models or for subgroup analyses.

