#### **14.1.4 Subgroup Analyses of ARR**

The subgroup analyses of the primary endpoint (at Month 24 for the ARR during the follow-up period) will be conducted on the FAS population.

A subgroup analysis at Month 24 of the ARR during the follow-up period for patients completing the study and patients who drop out will be performed. Estimates and CIs for the 2 subgroups will be reported using the same method as the primary analysis. This analysis will be repeated

considering the ARR based on all reported relapses, as described in the sensitivity analysis of the primary endpoint.

The same analysis will be performed for patients who complete treatment and for patients who do not complete treatment (i.e., completing Year 1 treatment but not Year 2 treatment) when the number of patients in the last group is greater than 10. This analysis will be repeated considering the ARR based on all the reported relapses, as described in the sensitivity analysis of the primary endpoint.

A subgroup analysis at Month 24 of the ARR during the follow-up period will be performed with reference to the type of MS at screening (RRMS, aSPMS, PPMS, and CIS). This analysis will be repeated considering the ARR based on all the reported relapses, as described in the sensitivity analysis of the primary endpoint.

For the primary outcome, the patterns of missingness will be explored. When the number of missing values is substantial (>5%), multiple imputation methodology will be considered for the analysis of the primary objective. At least 20 imputed datasets will be considered. The ARR at Month 24 for a patient will be considered missing if, for that patient, the number of relapses at Month 24 is missing or if the time on study for that patient is missing.

At least the following variables will be considered in the imputation model:

- ARR at Month 24
- Type of MS at screening
- Number of relapses in the previous 2 years
- Age
- Sex
- Baseline body mass index (BMI)
- Compliance

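### The SAP's time to cladribine discontinuation is time to last dose: a patient who completes Year 1, is recorded as discontinued and never starts Year 2 becomes an event at about Month 1.1

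*SAP*

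**What the plan says.** SAP section 13 (Study Dose Compliance and Exposure) defines elapsed time to discontinuation as the discontinuation date minus the date of first dose. It takes the discontinuation date from the last administration date on the treatment termination form, which "will be used as the date of discontinuation of cladribine tablets both for patients discontinuing the treatment early and for patients who complete treatment". For completers this date is a censoring date; no other group is named as censored. The result is summarized as a continuous variable and by Kaplan-Meier. SAP section 9 plans Kaplan-Meier estimates at fixed times, for example every 6 months.

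On the dosing calendar, Protocol 9.2.2 says that each yearly course "consists of 2 treatment weeks, 1 at the beginning of the first month and 1 at the beginning of the second month" of that year, with 4 or 5 dosing days per treatment week. Protocol 9.2.4 anticipates that "patients may not receive their second course of cladribine tablets precisely 12 months after the initiation of cladribine tablets". SAP section 6 says that if Year 2 is delayed, "all Year 2 visits and procedures will be moved out accordingly (at most 6 months".

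The SAP expects patients who stop between the courses. Section 8.2 defines a subgroup not completing treatment that includes those "completing Year 1 treatment but not Year 2 treatment", and section 14.1.4 analyzes relapse rate in patients who "do not complete treatment (i.e., completing Year 1 treatment but not Year 2 treatment".

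Protocol 9.1.2.2 lists elapsed time to discontinuation after first dose as a sub-item of a secondary outcome. It does not define the date of discontinuation.

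**The concern.** For a drug taken every day, the last dose is a fair stand-in for the moment of stopping. Here a patient who is fully on schedule takes nothing for about eleven months after the second treatment week. If that patient later does not start Year 2 and is recorded as discontinued, the SAP places the event at the end of the Year 1 course, when the patient was doing exactly what was planned. The label says time to discontinuation; for these patients the content is time to last dose.

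What is at stake is the reading of one descriptive secondary result. An early drop in the curve would be taken as patients giving up cladribine within weeks, when the stop may have been settled a year or more later.

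**Working it through.** The documents state no figure for this outcome, so there is nothing to reproduce. The check is date arithmetic followed by a product-limit calculation.

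**Inputs.** One month = 30.4375 days (SAP section 9). The second treatment week starts one month after the first and has 4 or 5 dosing days (Protocol 9.2.2). Year 2 may be delayed by at most 6 months (SAP section 6). Shares of patients are assumptions.

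**Event date for a Year-1-only discontinuer.** Elapsed time = gap between weeks + (dosing days − 1).
- 4 days: 30.4375 + 3 = 33.4 days = 1.10 months.
- 5 days: 30.4375 + 4 = 34.4 days = 1.13 months.
- With the gap varied from 28 to 31 days, the range is 31 to 35 days, or 1.02 to 1.15 months.

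**Dating error, from day 34.**

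| Stop actually settled | Calculation | Error |
|---|---|---|
| Right after the Year 1 course | – | near 0 |
| Month 6 | 182.6 − 34 = 148.6 days | 4.9 months |
| Planned Year 2 start | 365.25 − 34 = 331.25 days | 10.9 months |
| End of a 6-month delay | 547.9 − 34 = 513.9 days | 16.9 months |

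**Effect on the curve at Month 6.** Let a share e stop within the Year 1 course and a share q complete Year 1 but stop at or after the planned Year 2 start, with nobody censored before Month 6.
- Dated when the stop occurred: 1 − e.
- Under the SAP rule: 1 − e − q.
- Gap: (1 − e) − (1 − e − q) = q, whatever e is.
- For q = 0.05, 0.10 or 0.20, the gap is 0.05, 0.10 or 0.20. With e = 0.05 and q = 0.10: 0.95 against 0.85.
- If half of the Year-1-only group stops right after the Year 1 course, the gap halves.

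**Effect on the mean and median (assumed example, 100 patients).** Take 10 who never start Year 2 and stop at its planned start, 80 on-time completers, 9 completers delayed 6 months, and 1 who stops after the first week of a delayed Year 2 course.
- Last dose for on-time completers: (365 + 34)/30.4375 = 13.1 months; for delayed completers, 19.1 months.
- The single late stop: (365 + 182.6 + 4)/30.4375 = 18.12 months.
- Discontinuers only, SAP rule: (10 × 1.12 + 18.12)/11 = 2.7 months, median 1.1.
- Discontinuers only, the ten dated at the planned Year 2 start: (10 × 11.99 + 18.12)/11 = 12.5 months, median 12.0.
- All 100 patients, SAP rule: (10 × 1.12 + 18.12 + 80 × 13.1 + 9 × 19.1)/100 = 12.5 months, median about 13.1.

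The contrast in the mean and median therefore depends on who enters the continuous summary, which SAP section 13 does not say.

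**Why events cannot be re-dated alone.** If Year-1-only events were moved to Month 18 while all other patients were completers censored at about Month 13.1, only discontinuers would remain at risk and the estimate would fall to 0. Event and censoring dates must change together.

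**The case against.** The rule is explicit and deliberate: the SAP's modification history shows the definition of the discontinuation date being added in version 3.0. The protocol leaves the date undefined, so nothing is contradicted. Last exposure is a defensible convention for a drug given in short courses, and it is reasonable for a stop within a course. The result is descriptive, with no comparator or test. The planned listings show tablets and reasons for no dose by patient and visit, so a careful reader could pick out Year-1-only patients. All of this stands and limits the seriousness. It does not remove the mismatch between label and content, and no other rule in either document corrects the date.

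Two stronger readings are tempting.
- A reader might infer that the mean and median will certainly show very early stopping. The documents do not support this: over all patients in the example above, the SAP-rule mean is about 12.5 months.
- A reader might infer a substantial error late in the curve. In the same example, the single stop at 18.1 months occurs with 10 at risk and takes the SAP-rule estimate from 0.90 to 0.81, against 0.89 with events re-dated and completers kept event-free. That difference comes from one assumed patient, and nobody is at risk after about Month 19. The SAP plans to show numbers at risk, so the thin tail would be visible.

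The objection to full re-dating also has weight. SAP section 13 names "medication stop dates, medication dose (mg), number of doses, and reasons for discontinuation, if applicable", but neither document lists a decision date or a recorded delay among the data collected. Protocol 9.2.4 also allows Year 2 to slip for clinical factors other than lymphocyte count.

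**Conclusion.** The concern holds for patients who complete Year 1, are recorded as discontinued and never start Year 2. Each becomes an event at about Month 1.1, provided both Year 1 treatment weeks are taken on schedule. For them the analysis does not measure the protocol's time to discontinuation. The Month 6 estimate is too low by the share q who stop at or after the planned Year 2 start; q is unknown, and 0.05 to 0.20 is an assumed range.

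The proportion discontinuing, the reasons, the percentage of planned doses and the annualized relapse rate do not use this date and are unaffected.

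One limit remains. The termination form is not reproduced, and SAP section 13 names only early discontinuers and completers, so how deaths or losses between the courses are classed cannot be determined. The change should be made, but it does not threaten the primary result.

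**What to change.** In SAP section 13:

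1. Label the Kaplan-Meier and continuous summaries 'time to last dose'.
2. State that the continuous summary covers discontinuers only.
3. Add a table of the proportion of patients completing each of the four treatment weeks, from exposure data already collected.

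This costs a label, a sentence and one table, with no new data. If the analysis is already complete, SAP section 4 allows unplanned analyses that are clearly identified in the study report.

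Optionally, add a supplementary time-to-discontinuation analysis with both dates changed together. Date Year-1-only discontinuers at a recorded decision date if the form has one, and otherwise at the earlier of the start of another MS drug and the planned Year 2 start. Protocol 9.3 provides the former through its "Medication log containing other MS DMD treatments (if applicable) during the study period, including medication doses and routes of administration, start dates". Keep completers event-free to the end of follow-up; keep the last-dose date for stops within a course.

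The supplementary analysis needs some reprogramming and has its own artefact. Without a decision date, events will cluster at about Month 12, and some patients still waiting for a delayed course may be dated too early. Footnote the share of events dated by convention.
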